4.7 Other outcomes

The following binary (yes/no) outcomes⁴ (appendix C) will be summarised descriptively, where available.

- Blood Transfusion
- Iron therapy

4.8 Additional outcomes

We will explore the composite outcome of non-fatal bleeding and all-cause mortality. This will be analysed using the same approach as for the primary outcome in section 4.5. The number and proportions of participants with an event for the individual components of the outcome will be reported alongside the composite.

4.9 Extended follow-up

The analyses of the primary and secondary outcomes will be repeated censoring at the date of last available follow-up.

⁴ The Haemoglobin outcome in the protocol will not be analysed, as the data is not nationally linked.

5. Validation and QC

The following will be done by a second statistician:

1. The code will be checked and run to ensure results are as stated
2. Check of data fidelity from raw data to SAS data files (random selection)
3. Check treatment allocation consistent between UK and NZ datasets
4. Check of ICD10/OPCS4 (or equivalents codes) in SMR01 (or equivalent datasets) map to the study SAP
5. The statistical report will be read and sense-checked.

6. Data sharing

Data will be stored inside a Trusted Research Environment (TRE) managed by AIMES on behalf of ECTU for 12 years. Access to the data needs to be approved, there are no data sharing agreements, protocols or contracts in place or planned.

7. References

1. Royston, P. and M.K. Parmar, *The use of restricted mean survival time to estimate the treatment effect in randomized clinical trials when the proportional hazards assumption is in doubt*. Stat Med, 2011. **30**(19): p. 2409-21.
2. Burke, D.L., J. Ensor, and R.D. Riley, *Meta-analysis using individual participant data: one-stage and two-stage approaches, and why they may differ*. Statistics in Medicine, 2017. **36**(5): p. 855-875.
<https://doi.org/10.2307/2670170>

Appendix A

Operation code identified following date of MI in ANY position. It will be assumed those with none of the following codes recorded will be classed as medically managed.

Data sources: Scotland: SMR00/SMR01 England: Hospital Episode Statistics

Code	Procedure	Cardiac history group
OPCS4 K75.1	Percutaneous transluminal balloon angioplasty and insertion of 1–2 drug-eluting stents into coronary artery	Coronary angioplasty with drug eluting stent
OPCS4 K75.2	Percutaneous transluminal balloon angioplasty and insertion of 3 , more drug-eluting stents into coronary artery	
OPCS4 K75.3	Percutaneous transluminal balloon angioplasty and insertion of 1–2 stents into coronary artery (stent not specified)	Coronary angioplasty – stent type not specified
OPCS4 K75.4	Percutaneous transluminal balloon angioplasty and insertion of 3 , more stents into coronary artery (stent not specified)	
OPCS4 K75.3 , K75.4, Y14.1 , Y14.2 , Y14.3	Percutaneous transluminal balloon angioplasty and insertion of stent (other than drug-eluting stent).	Coronary angioplasty with bare metal stent

Code	Procedure	Cardiac history group
OPCS4 K40	Saphenous vein graft of coronary artery	Coronary artery bypass graft surgery
OPCS4 K41	Other autograft replacement of coronary artery	
OPCS4 K42	Allograft replacement of coronary artery	
OPCS4 K43	Prosthetic replacement of coronary artery	
OPCS4 K44	Other replacement of coronary artery	
OPCS4 K45	Connection of thoracic artery to coronary artery	
OPCS4 K46	Other bypass of coronary artery	
OPCS4 K48	Other open operation on coronary artery	

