5.5 RANDOMISATION

5.5.1 Randomisation Procedures

A web-based computer-generated randomisation process will be used to ensure allocation concealment and reduce bias. The randomisation system will be provided by ECTU and patients will be randomised using their unique health identifier to prevent inadvertent duplicate randomisation. International sites will use their own randomisation system which will be described in their country specific protocol. Randomisation will be by permuted-block with a level of stratification for

each of the following groups of patients: (i) conservative non-invasive strategy (invasive coronary angiography is not planned), (ii) invasive coronary angiography is planned but has not yet occurred, (iii) an invasive coronary angiogram has been performed and the patient has been referred or undergone CABG surgery, (iv) an invasive coronary angiogram has been performed and the patient has had at least one drug eluting stent implanted, (v) an invasive coronary angiogram has been performed and the patient has had only bare metal stents implanted (this group will also include patients who have had balloon angioplasty only performed without stent implantation), (vi) an invasive coronary angiogram has been performed and the patient is to receive medical management only.

Block size will be randomly determined, and each block will contain both treatments in a 1:1 ratio.

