Appendix B

Baseline characteristics defined as follows using the following codes in ANY position in the 10 years prior to the date of index MI (or date of admission for index MI). If code is not identified in any admissions then they will be assumed to not have the variable of interest.

Data sources

Scotland: SMR00 / SMR01 / Prescribing Information System / SCI-Diabetes

England: Hospital Episode Statistics / Medicines dispensed in Primary Care (NHSBSA data)

Variable	Code (ICD-10 , OPCS4)
IMD	Index of Multiple Deprivation
Ethnicity	Ethnicity
Cardiovascular risk factors	
Smoking history	Z87.891x (including Z812 / Z720/T652/F17x)
Hypertension	Previously prescribed AntiHypertensiveTherapy Approved drug names: ATENOLOL, ATENOLOL WITH NIFEDIPIN, BISOPROLOL FUMARATE, CARVEDILOL, LABETALOL HYDROCHL, AMLODIPINE AND VALSARTAN, CANDESARTAN CILEXETIL, CAPTOPRIL, CO-ZIDOCAPT, ENALAPRIL MALEATE, ENALAPRIL MALEATE WITH, EPROSARTAN MESILATE, FOSINOPRIL, IRBESARTAN, IRBESARTAN AND HYDROCHL, LISINOPRIL, LISINOPRIL AND HYDROCHL, LOSARTAN POTASSIUM, LOSARTAN WITH HYDROCHL, OLMESARTAN MEDOXOMIL, PERINDOPRIL, PERINDOPRIL WITH AMLODI, PERINDOPRIL WITH INDAPA, QUINAPRIL, QUINAPRIL HYDROCHL, RAMIPRIL, TELMISARTAN, TELMISARTAN AND HYDROCHL, TRANDOLAPRIL, VALSARTAN, VALSARTAN AND HYDROCHL, AMLODIPINE, FELODIPINE, LERCANIDIPINE, DOXAZOSIN, BENDROFLUMETHIAZIDE.
Diabetes Mellitus	E10x, E11x, E12x, E13x, E14x,

	Previously prescribed AntiHyperglycaemics Approved drug names: METF,MIN, REPAGLINIDE, PIOGLITAZONE, ROSIGLITAZONE, SITAGLIPTIN, SAXAGLIPTIN, VILDAGLIPTIN, ALOGLIPTIN, LINAGLIPTIN, GLIPIZIDE, DAPAGLIFLOZIN, EMPAGLIFLOZIN, CANAGLIFLOZIN, GLIBENCLAMIDE, REPAGLINIDE, TOLBUTAMIDE, EXENATIDE, LIRAGLUTIDE, SEMAGLUTIDE, INSULIN
Hyperlipidaemia	Previously prescribed LipidLoweringTherapy Approved drug names: ATORVASTATIN, BEZAFIBRATE, CIPROFIBRATE, EZETIMIBE, EZETIMIBE AND SIMVASTATIN, FENOFLIBRATE, FLUVASTATIN, GEMFIBROZIL, PRAVASTATIN, ROSUVASTATIN, SIMVASTATIN
Other medical history	
Ischaemic heart disease	I20x, I21x, I22x, I23x, I24x, I25x,
Myocardial infarction	I21x, I22x,
Percutaneous coronary intervention	Z98.61x OPCS4 codes: K50x, K75x, K49x
Coronary artery bypass grafting	Z95.1x, OPCS4 codes K40x, K41x, K42x, K43x, K44x, K45x, K46x, K47x, K48x
Heart failure	I50x

Ischaemic stroke	I63x
Haemorrhagic stroke	I60x, I61x, I62x
Chronic kidney disease	N18x, N19x
Medications at presentation	
Aspirin	Previously prescribed Aspirin Approved drug names: ASPIRIN

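### SAP Appendix A omits procedure codes that Appendices B and C count as coronary intervention, so some treated patients awaiting angiography at randomisation would default to medically managed

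*SAP*

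**What the plan says.** SAP 4.3 and 4.5.3 use Appendix A for one purpose: to decide which group a stratum (ii) patient belongs to once the angiogram has been done. Appendix A looks for listed operation codes after the date of MI, in any position, and closes with a default: "It will be assumed those with none of the following codes recorded will be classed as medically managed". Its codes are K75.1 to K75.4, Y14.1 to Y14.3, K40 to K46, and K48. Every PCI row describes insertion of a stent.

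Appendix B defines previous PCI by "OPCS4 codes: K50x, K75x, K49x" and previous bypass grafting by "OPCS4 codes K40x, K41x, K42x, K43x, K44x, K45x, K46x, K47x, K48x", alongside a status code for each. Appendix C defines the coronary revascularisation outcome by K40x to K50x and K75x.

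Protocol 5.5.1 describes stratum (v), the bare metal stratum, and adds that "this group will also include patients who have had balloon angioplasty only performed without stent implantation". The SAP's own lists of the strata (sections 1 and 4.3) leave that clause out.

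On stent type, Appendix A gives K75.3 and K75.4 the group "Coronary angioplasty – stent type not specified". It then lists them again in the bare metal row, as "OPCS4 K75.3 , K75.4, Y14.1 , Y14.2 , Y14.3".

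**The concern.** A default rule is only as good as the list it falls back from. Here the same SAP treats certain codes as intervention in two appendices and, by omission, as no intervention in the third. A stratum (ii) patient whose only procedure code after the MI is one of these would be counted as medically managed. If the procedure is the main one recorded and falls after the index discharge, the same patient would also count as revascularised in a secondary outcome.

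What is at stake is the meaning of the medical group in the pre-specified cohorts (protocol 9.3, SAP 4.5.3). Treated patients would sit on the wrong side of the contrast between medical management and intervention. Balloon-only patients would be handled differently according to when they were randomised: with bare metal stents if already treated, with medical management if still awaiting angiography.

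**Working it through.** No sample size, power or event figure is involved. The check compares code lists.

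| Code | Appendix A | Appendix B | Appendix C, revascularisation |
|---|---|---|---|
| K40–K46, K48 | bypass | bypass | yes |
| K47 | absent, so medically managed | bypass | yes |
| K49, K50 | absent, so medically managed | PCI | yes |
| K75.1, K75.2 | drug-eluting stent | PCI | yes |
| K75.3, K75.4 | type not specified; also in the bare metal row with Y14.1–Y14.3 | PCI | yes |
| other K75 subcodes | absent, so medically managed | PCI | yes |

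1. **Code families.** Appendix B has K40–K48 (9) plus K49, K50 and K75 (3), which makes 12. Appendix C has the same 12. Appendix A has K40–K46 (7), K48 (1) and K75 (1), which makes 9. The difference is 12 − 9 = 3 families: K47, K49 and K50.
2. **Within K75.** Appendices B and C take the whole family; Appendix A takes only .1 to .4.
3. **Default rule.** A patient whose only code is K47, K49, K50 or another K75 subcode matches no row and is classed as medically managed.
4. **Balloon-only patients.** No Appendix A row covers PCI without a stent, so a patient treated by balloon alone has no row to match. Protocol 5.5.1 puts such patients in stratum (v).
5. **Fallback groups in SAP 4.5.3.** The any-intervention group merges the two stent groups and bypass surgery. A patient already defaulted to medical management stays outside it, so merging does not repair the error.
6. **Quality control.** SAP section 5 has a second statistician check that codes map to the SAP. A gap in the SAP's own list would pass that check.
7. **Where the error cannot reach.** The primary Cox model adjusts for the randomisation stratum (SAP 4.5), not the Appendix A group. SAP 4.5.3 also runs the subgroup analysis without stratum (ii). Patients already treated at randomisation have a recorded stratum.
8. **Context for size.** Protocol 9.1 expects bypass and bare metal patients together to be just under 7.5%. If that share held among the 4,576 UK patients, it gives 0.075 × 4,576 ≈ 343 people across both groups and both arms. This is not a count of affected patients, which the documents do not give. It shows only that these groups are small enough for a few misplaced patients to be visible.

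**The case against.** The strongest case against has four parts.

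- **Narrow reach.** Appendix A touches one descriptive baseline line and one of two versions of an exploratory subgroup analysis, and the other version is already pre-specified. This stands and sets the weight of the point. A reader might infer that treated patients enter the medical group throughout the trial, or that the primary result is exposed; the documents support neither.
- **Different purposes.** Appendix B captures history and Appendix C outcomes, so their lists need not equal Appendix A's. Protocol 9.3 and SAP 4.5.3 also name the bare metal cohort without mentioning balloon angioplasty. Both are true, but neither gives a reason to call a patient with a PCI or bypass code medically managed, and the protocol's stratum definition says where balloon-only patients belong.
- **What the codes mean.** The documents class K49 and K50 only as PCI and never as balloon-only. This stands. A reader might infer that both families can simply be moved to the bare metal group, but that would go beyond the text.
- **The K75.3/K75.4 rows.** The bare metal row plausibly means K75.3 or K75.4 combined with a Y14 code, in which case the two rows separate cleanly. A reader might infer that the double listing helps push patients into medical management. It does not, since both rows are PCI groups. Nor do the documents say that patients with an unspecified stent are dropped. What remains is that the combination rule is not written down and that the unspecified group matches none of the four subgroups.

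It is also no defect that stratum (ii) patients are grouped from a different source: they had no angiogram result at randomisation, and the SAP discloses this.

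**Conclusion.** The concern holds as a minor error in the plan as written. Followed literally, Appendix A classes some treated stratum (ii) patients as medically managed, against Appendices B and C and, for balloon-only patients, against protocol 5.5.1. The cause is the omitted codes together with the default rule. The effect is confined to the baseline summary for stratum (ii) and to the subgroup analysis that includes it.

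The number of patients is unknown and may be small. The conclusion assumes that at least some stratum (ii) patients carry an omitted code with no listed code beside it, which the documents neither confirm nor exclude. The K75.3/K75.4 wording is a separate matter of clarity.

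**What to change.** In Appendix A:

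- Add K47 to the bypass group.
- Add K49, K50 and the remaining K75 subcodes as PCI, so that none falls to the default.
- Have the sponsor confirm which of these are stent-free, and place those with the bare metal and balloon group as in protocol 5.5.1. Restore the balloon clause in the SAP's lists of strata.

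As a separate clarification:

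- State that K75.3 and K75.4 count as bare metal only with a Y14.1, Y14.2 or Y14.3 code.
- Say in SAP 4.5.3 that the remaining unspecified stents are included in the any-stent group.

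The cost is an edit to a code list and a few lines of SAP text, using data already linked. It is best made before the subgroup results are seen, so that membership is not left to the analyst.

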Appendix B

Baseline characteristics defined as follows using the following codes in ANY position in the 10 years prior to the date of index MI (or date of admission for index MI). If code is not identified in any admissions then they will be assumed to not have the variable of interest.

Data sources

Scotland: SMR00 / SMR01 / Prescribing Information System / SCI-Diabetes

England: Hospital Episode Statistics / Medicines dispensed in Primary Care (NHSBSA data)

Variable	Code (ICD-10 , OPCS4)
IMD	Index of Multiple Deprivation
Ethnicity	Ethnicity
Cardiovascular risk factors	
Smoking history	Z87.891x (including Z812 / Z720/T652/F17x)
Hypertension	Previously prescribed AntiHypertensiveTherapy Approved drug names: ATENOLOL, ATENOLOL WITH NIFEDIPIN, BISOPROLOL FUMARATE, CARVEDILOL, LABETALOL HYDROCHL, AMLODIPINE AND VALSARTAN, CANDESARTAN CILEXETIL, CAPTOPRIL, CO-ZIDOCAPT, ENALAPRIL MALEATE, ENALAPRIL MALEATE WITH, EPROSARTAN MESILATE, FOSINOPRIL, IRBESARTAN, IRBESARTAN AND HYDROCHL, LISINOPRIL, LISINOPRIL AND HYDROCHL, LOSARTAN POTASSIUM, LOSARTAN WITH HYDROCHL, OLMESARTAN MEDOXOMIL, PERINDOPRIL, PERINDOPRIL WITH AMLODI, PERINDOPRIL WITH INDAPA, QUINAPRIL, QUINAPRIL HYDROCHL, RAMIPRIL, TELMISARTAN, TELMISARTAN AND HYDROCHL, TRANDOLAPRIL, VALSARTAN, VALSARTAN AND HYDROCHL, AMLODIPINE, FELODIPINE, LERCANIDIPINE, DOXAZOSIN, BENDROFLUMETHIAZIDE.
Diabetes Mellitus	E10x, E11x, E12x, E13x, E14x,

	Previously prescribed AntiHyperglycaemics Approved drug names: METF,MIN, REPAGLINIDE, PIOGLITAZONE, ROSIGLITAZONE, SITAGLIPTIN, SAXAGLIPTIN, VILDAGLIPTIN, ALOGLIPTIN, LINAGLIPTIN, GLIPIZIDE, DAPAGLIFLOZIN, EMPAGLIFLOZIN, CANAGLIFLOZIN, GLIBENCLAMIDE, REPAGLINIDE, TOLBUTAMIDE, EXENATIDE, LIRAGLUTIDE, SEMAGLUTIDE, INSULIN
Hyperlipidaemia	Previously prescribed LipidLoweringTherapy Approved drug names: ATORVASTATIN, BEZAFIBRATE, CIPROFIBRATE, EZETIMIBE, EZETIMIBE AND SIMVASTATIN, FENOFLIBRATE, FLUVASTATIN, GEMFIBROZIL, PRAVASTATIN, ROSUVASTATIN, SIMVASTATIN
Other medical history	
Ischaemic heart disease	I20x, I21x, I22x, I23x, I24x, I25x,
Myocardial infarction	I21x, I22x,
Percutaneous coronary intervention	Z98.61x OPCS4 codes: K50x, K75x, K49x
Coronary artery bypass grafting	Z95.1x, OPCS4 codes K40x, K41x, K42x, K43x, K44x, K45x, K46x, K47x, K48x
Heart failure	I50x

Ischaemic stroke	I63x
Haemorrhagic stroke	I60x, I61x, I62x
Chronic kidney disease	N18x, N19x
Medications at presentation	
Aspirin	Previously prescribed Aspirin Approved drug names: ASPIRIN
Clopidogrel	Previously prescribed Clopidogrel Approved drug names: Clopidogrel
Prasugrel	Previously prescribed Prasugrel Approved drug names: Prasugrel
Ticagrel	Previously prescribed Ticagrel, Approved drug names: Ticagrel,
Lipid lowering therapy	Previously prescribed LipidLoweringTherapy Approved drug names: ATORVASTATIN, BEZAFIBRATE, CIPROFIBRATE, EZETIMIBE, EZETIMIBE AND SIMVASTATIN, FENOFLIBRATE, FLUVASTATIN, GEMFIBROZIL, PRAVASTATIN, ROSUVASTATIN, SIMVASTATIN
Beta-blocker	Previously prescribed BetaBlocker Approved drug names: ACEBUTOLOL, ATENOLOL, ATENOLOL WITH NIFEDIPIN, BISOPROLOL FUMARATE, CARVEDILOL, CELIPOLOL HYDROCHL, CO-TENIDONE, LABETALOL HYDROCHL, METOPROLOL TARTRATE, NADOLOL, NEBIVOLOL, OXPRENOLOL HYDROCHL, PINDOLOL, PROPRANOLOL HYDROCHL, TIMOLOL MALEATE

Angiotensin converting enzyme inhibitor , angiotensin receptor blockers	Previously prescribed ACEInhibitorARB Approved drug names: AMLODIPINE AND VALSARTAN, CANDESARTAN CILEXETIL, CAPTOPRIL, CO-ZIDOCAPT, ENALAPRIL MALEATE, ENALAPRIL MALEATE WITH, EPROSARTAN MESILATE, FOSINOPRIL, IRBESARTAN, IRBESARTAN AND HYDROCHL, LISINOPRIL, LISINOPRIL AND HYDROCHL, LOSARTAN POTASSIUM, LOSARTAN WITH HYDROCHL, OLMESARTAN MEDOXOMIL, PERINDOPRIL, PERINDOPRIL WITH AMLODI, PERINDOPRIL WITH INDAPA, QUINAPRIL, QUINAPRIL HYDROCHL, RAMIPRIL, TELMISARTAN, TELMISARTAN AND HYDROCH, TRANDOLAPRIL, VALSARTAN, VALSARTAN AND HYDROCHL
oral anticoagulants	Previously prescribed OralAnticoagulant Approved drug names: ACENOCOUMAROL, APIXABAN, DABIGATRAN ETEXILATE, PHENINDIONE, RIVAROXABAN, WARFARIN SODIUM, EDOXABAN

Appendix C

Outcomes defined used the following codes and positions specified below following the date of index MI unless otherwise specified. If the code is not identified in any admissions/deaths then they will be assumed to not have the outcome of interest.

Data sources

Scotland: SMR00 / SMR01 / NRS Deaths / Prescribing Information System / Scottish Blood Transfusion Database

England: Hospital Episode Statistics / Civil Registrations of Death / Medicines dispensed in Primary Care (NHSBSA data)

Outcome	Code (ICD-10 , OPCS4)
All-cause mortality	Any record of death.
Non-cardiovascular death (including fatal bleeding) and major non-fatal bleeding	
Death due to a non-cardiovascular cause
 
Primary position for cause of death
 
Ax, Bx, Cx, Dx Ex, Fx , Gx , Hx , Jx, Kx , Lx , Mx , Nx , Ox , Px , Qx , Rx , Sx , Tx , Ux , Vx , Xx , Yx , Zx.
 
OR
 
Hospitalisation for bleeding
 
Primary or first secondary position
 
I60x, I61x, I62x, S06.4x, S06.5x, S06.6x, K92.0x, K92.1x, K 92.2x, I85.0x, I98.3x, K22.6x, K25.0x, K25.2x, K25.4x, K25.6x, K26.0x, K26.2x, K26.4x, K26.6x, K27.0x, K27.2x, K27.4x, K27.6x, K28.0x, K28.2x, K28.4x, K28.6x, K29.0x, K62.5x, K66.1x, R58x, I23.0x, I31.2x, I69.0x, I69.1x, I69.2x, H21x, H35.6x, H31.3x, H43.1x, H44.8x, H45.0x, R04.0x, R04.1x, R04.2x, R04.8x, R04.9x, T81.0x, D62x, N83.7x, N93.8x , N93.9x, O03.1x, O03.6x, O04.1x, O04.6x, O05.1x, O05.6x, O06.1x, O06.6x, O20.8x, O20.9x, O46x , O67x, O07.1x, O07.6x, O08.1x, O71.7x , O72.0x , O72.1x , O72.2x , O90.2x , P26.1x , R31x , M25.0x.
 
OR

	
Primary procedure position (OPSC4)
 
E05x , E058x , E059x , F162x , D041x , E203x , F365x , G523x , H212x , H531x , K681x , P093x , P271x , T301x , Y221x , T032x , Y221x , T032x , Y321x , V032x , A052x , A053x , A054x , A103x , A401x , A411x

Non-cardiovascular death (including fatal bleeding)	
Primary cause of death
 
Ax , Bx , Cx , Dx , Ex , Fx , Gx , Hx , Jx , Kx , Lx , Mx , Nx , Ox , Px , Qx , Rx , Sx , Tx , Ux , Vx , Xx , Yx , Zx

Major fatal and non-fatal bleeding	
Hospitalisation for bleeding
 
Primary or first secondary position
 
I60x, I61x, I62x, S06.4x, S06.5x, S06.6x, K92.0x, K92.1x, K 92.2x, I85.0x, I98.3x, K22.6x, K25.0x, K25.2x, K25.4x, K25.6x, K26.0x, K26.2x, K26.4x, K26.6x, K27.0x, K27.2x, K27.4x, K27.6x, K28.0x, K28.2x, K28.4x, K28.6x, K29.0x, K62.5x, K66.1x, R58x, I23.0x, I31.2x, I69.0x, I69.1x, I69.2x, H21x, H35.6x, H31.3x, H43.1x, H44.8x, H45.0x, R04.0x, R04.1x, R04.2x, R04.8x, R04.9x, T81.0x, D62x, N83.7x, N93.8x , N93.9x, O03.1x, O03.6x, O04.1x, O04.6x, O05.1x, O05.6x, O06.1x, O06.6x, O20.8x, O20.9x, O46x , O67x, O07.1x, O07.6x, O08.1x, O71.7x , O72.0x , O72.1x , O72.2x , O90.2x , P26.1x , R31x , M25.0x.
 
OR
 
Primary procedure position (OPCS4)
 
E05x , E058x , E059x , F162x , D041x , E203x , F365x , G523x , H212x , H531x , K681x , P093x , P271x , T301x , Y221x , T032x , Y221x , T032x , Y321x , V032x , A052x , A053x , A054x , A103x , A401x , A411x
 
OR
 
Death due to bleeding
 
Primary cause of death

	I60x, I61x, I62x, S06.4x, S06.5x, S06.6x, K92.0x, K92.1x, K 92.2x, I85.0x, I98.3x, K22.6x, K25.0x, K25.2x, K25.4x, K25.6x, K26.0x, K26.2x, K26.4x, K26.6x, K27.0x, K27.2x, K27.4x, K27.6x, K28.0x, K28.2x, K28.4x, K28.6x, K29.0x, K62.5x, K66.1x, R58x, I23.0x, I31.2x, I69.0x, I69.1x, I69.2x, H21x, H35.6x, H31.3x, H43.1x, H44.8x, H45.0x, R04.0x, R04.1x, R04.2x, R04.8x, R04.9x, T81.0x, D62x, N83.7x, N93.8x , N93.9x, O03.1x, O03.6x, O04.1x, O04.6x, O05.1x, O05.6x, O06.1x, O06.6x, O20.8x, O20.9x, O46x , O67x, O07.1x, O07.6x, O08.1x, O71.7x , O72.0x , O72.1x , O72.2x , O90.2x , P26.1x , R31x , M25.0x.
Hospitalisation for bleeding	
Hospitalisation for bleeding
 
Primary or first secondary position
 
I60x, I61x, I62x, S06.4x, S06.5x, S06.6x, K92.0x, K92.1x, K 92.2x, I85.0x, I98.3x, K22.6x, K25.0x, K25.2x, K25.4x, K25.6x, K26.0x, K26.2x, K26.4x, K26.6x, K27.0x, K27.2x, K27.4x, K27.6x, K28.0x, K28.2x, K28.4x, K28.6x, K29.0x, K62.5x, K66.1x, R58x, I23.0x, I31.2x, I69.0x, I69.1x, I69.2x, H21x, H35.6x, H31.3x, H43.1x, H44.8x, H45.0x, R04.0x, R04.1x, R04.2x, R04.8x, R04.9x, T81.0x, D62x, N83.7x, N93.8x , N93.9x, O03.1x, O03.6x, O04.1x, O04.6x, O05.1x, O05.6x, O06.1x, O06.6x, O20.8x, O20.9x, O46x , O67x, O07.1x, O07.6x, O08.1x, O71.7x , O72.0x , O72.1x , O72.2x , O90.2x , P26.1x , R31x , M25.0x.
 
OR
 
Primary procedure position (OPCS4)
 
E05x , E058x , E059x , F162x , D041x , E203x , F365x , G523x , H212x , H531x , K681x , P093x , P271x , T301x , Y221x , T032x , Y221x , T032x , Y321x , V032x , A052x , A053x , A054x , A103x , A401x , A411x

Intracranial haemorrhage	
Intracranial haemorrhage event
 
Primary or first secondary position
 
I60x , I61x , I62x , S06.5x , S06.6x.

	
OR
 
Death due to intracranial haemorrhage
 
Primary cause of death
 
I60x , I61x , I62x , S06.5x , S06.6x.

Gastrointestinal bleeding	
Gastrointestinal bleeding event
 
Primary or first secondary position
 
K92.0x , K92.1x , K 92.2x , I85.0x , I98.3x , K22.6x , K25.0x , K25.2x , K25.4x , K25.6x , K26.0x , K26.2x , K26.4x , K26.6x , K27.0x , K27.2x , K27.4x , K27.6x , K28.0x , K28.2x , K28.4x , K28.6x , K29.0x , K62.5x , K55.2x , K66.1x.
 
OR
 
Death due to Gastrointestinal bleeding
 
Primary cause of death
 
K92.0x , K92.1x , K 92.2x , I85.0x , I98.3x , K22.6x , K25.0x , K25.2x , K25.4x , K25.6x , K26.0x , K26.2x , K26.4x , K26.6x , K27.0x , K27.2x , K27.4x , K27.6x , K28.0x , K28.2x , K28.4x , K28.6x , K29.0x , K62.5x , K55.2x , K66.1x.

Cardiovascular mortality and non-fatal myocardial infarction	
Death due to a cardiovascular cause
 
Primary cause of death
 
Ix
 
OR
 
Myocardial infarction after the Index Admission Discharge Date

	
Primary or first secondary position
 
I21x, I22x

Cardiovascular mortality (cardiac and non-cardiac)	
Death due to a cardiovascular cause
 
Primary cause of death
 
Ix

Myocardial infarction (fatal and non- fatal)	
Myocardial infarction after the Index Admission Discharge Date
 
Primary or first secondary position
 
I21x, I22x
 
OR
 
Death due to myocardial infarction
 
Primary cause of death
 
I21x, I22x

Stent thrombosis	
Stent thrombosis
 
Primary or first secondary position
 
T82.8x

Coronary revascularisation	
Coronary revascularisation after the Index Admission Discharge Date
 
Primary procedure position (OPCS4)

	K40x, K41x, K42x, K43x, K44x, K45x, K46x, K47x, K48x, K49x, K50x, K75x.
Thrombotic stroke	
Ischaemic stroke
 
Primary or first secondary position
 
I63x
 
OR
 
Death due to ischaemic stroke
 
Primary cause of death
 
I63x

Blood transfusion	Any record of transfusion
Iron therapy	
Prescribed Iron Therapy
 
Approved drug names: FERROUS SULPHATE, FERROUS FUMARATE, FERROUS GLUCONATE, FERRIC MALTOL, FERROUS CALCIUM CITRATE, FERROUS GLYCINE SULFATE, IRON CARBOXYMALTOSE, SODIUM FEREDETATE, IRON CARBOXYMALTOSE, IRON DEXTRAN, IRON SUCROSE, VENOFER, FERINJECT

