1.4 PILOT DATA: ONE-YEAR MORTALITY FOLLOWING MYOCARDIAL INFARCTION

Clinical trial populations tend to be highly selected and hence do not reflect real world clinical practice. Using our national datasets, we have explored one-year mortality following acute coronary syndrome (Table 2). Perhaps as anticipated, all event rates are much higher in real world populations. Although cardiovascular death is 4-fold higher, the proportion of non-cardiovascular death is 8-fold higher and includes >3 -fold higher rates of fatal bleeding. This reinforces the need to address this question in the population that will be treated in routine clinical practice.

Table 2.
Comparative Event Rates Following Acute Coronary Syndrome

	CURE (Clopidogrel)	TRITON (Prasugrel)	TRILOGY (Prasugrel)	PLATO (Ticagrelor)	Randomised Controlled Trial Average	Scotland (Clopidogrel) 2006-2010 (one-year event rates)
All-cause Mortality	5.8%	3.0%	8.3%	4.5%	5.40%	25.4%
Cardiovascular Death	5.1%	2.1%	6.6%	4.0%	4.45%	17.8%
Non- cardiovascular Death	0.7%	0.9%	1.7%	0.5%	0.95%	7.6%
Fatal Bleeding	0.2%	0.4%	0.2%	0.3%	0.28%	0.9%

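### SAP Appendix C: W-coded deaths fall in neither cause-specific death endpoint, and ten I-coded bleeding deaths cannot enter the standalone non-cardiovascular endpoint labelled as including fatal bleeding

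*SAP*

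**What the plan says.** All places are in SAP Appendix C unless stated.

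- **All-cause mortality (primary outcome):** "Any record of death".
- **Non-cardiovascular death:** two rows, one standalone and one combined with major non-fatal bleeding. Both labels say that fatal bleeding is included. Each row types out the same letters for primary cause of death: "Gx , Hx , Jx, Kx , Lx , Mx" in the middle of the composite row, and "Tx , Ux , Vx , Xx , Yx , Zx" at the end of both.
- **Cardiovascular death:** "Death due to a cardiovascular cause", defined as any I code as primary cause. The same rule serves the composite with non-fatal myocardial infarction.
- **Bleeding deaths:** the endpoint for major fatal and non-fatal bleeding has its own list of primary causes, which begins "I60x, I61x, I62x, S06.4x, S06.5x, S06.6x, K92.0x, K92.1x, K 92.2x, I85.0x, I98.3x".
- **Unlisted codes:** the appendix treats a participant without a listed code as not having the outcome.
- **Censoring:** SAP 4.6 censors each secondary outcome at competing causes of death.

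In the protocol, Table 3 uses the same label for non-cardiovascular death. Section 1.4 says of the Scottish data that "the proportion of non-cardiovascular death is 8-fold higher and includes" a raised rate of fatal bleeding.

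**The concern.** There are two separate faults.

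The first is a gap. Once I is assigned to cardiovascular death, W is the only letter left over, and no catch-all picks it up. A death with a W primary cause is then a death for the primary outcome and a censored observation in both cause-specific analyses. A published table of cardiovascular and non-cardiovascular deaths could fail to add up to total deaths, with no stated reason.

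The second is a mismatch between label and codes. A reader of the standalone non-cardiovascular endpoint is told that it contains fatal bleeding. Part of what the SAP itself calls bleeding death is placed in the cardiovascular endpoints instead. This matters because the trial weighs bleeding harm against ischaemic benefit. If longer therapy causes more fatal bleeds, the I-coded ones leave a safety endpoint and enter two efficacy endpoints. The non-cardiovascular ratio is then pulled towards 1, and the cardiovascular ratio (3 v 12 months) is pushed slightly below 1.

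**Working it through.** **1. Letters.** Each non-cardiovascular row lists 24 of the 26 letters, and the missing two are I and W. Taking out I, which is cardiovascular death, leaves W. The two rows are punctuated differently and both go from V to X, so a PDF-reading artefact is unlikely.

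**2. Bleeding-death list.** It holds 76 distinct codes. Ten are I codes: I60, I61, I62, I85.0, I98.3, I23.0, I31.2, I69.0, I69.1 and I69.2. The other 76 - 10 = 66 can enter non-cardiovascular death. None is a W code.

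**3. Where a death counts, by primary cause.**

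| Primary cause | All-cause | Cardiovascular | Non-cardiovascular, standalone | Non-cardiovascular or major non-fatal bleeding | Major bleeding |
|---|---|---|---|---|---|
| W code | yes | no | no | only via a bleeding admission or procedure | only via a bleeding admission or procedure |
| I85.0 | yes | yes | no | only via a bleeding admission or procedure | yes |
| K25.0 | yes | no | yes | yes | yes |

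**4. The protocol's own split.** In Protocol Table 2, cardiovascular plus non-cardiovascular death equals all-cause mortality in every column: 5.1 + 0.7 = 5.8; 2.1 + 0.9 = 3.0; 6.6 + 1.7 = 8.3; 4.0 + 0.5 = 4.5; 4.45 + 0.95 = 5.40; 17.8 + 7.6 = 25.4. The SAP split does not guarantee this.

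**5. The plan's figures.** With two proportions, pooled variance, no continuity correction and 8,472 per group, 6% v 5% non-cardiovascular mortality gives 81.5% power (Protocol 9.2 states 81%), and 0.6% v 0.3% bleeding death gives 83.1% (stated 83%). These figures are not in dispute. The Scottish rates times 0.667 give cardiovascular 0.178 x 0.667 = 0.1187, non-cardiovascular 0.076 x 0.667 = 0.0507 and fatal bleeding 0.0092 x 0.667 = 0.0061. The first two sum to 0.1694, the planned 16.9%.

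**6. Size of the I-code effect.** Inputs are 4,576 / 2 = 2,288 per arm (UK only, equal split), fatal bleeding 0.6% (12 months) v 0.3% (3 months), and an I-coded share s of 25-75%. The share is an assumption, because the documents do not give it. Deaths moved are 2,288 x 0.006s v 2,288 x 0.003s. The 12-month arm has 2,288 x 0.0507 = 116 non-cardiovascular deaths. Risk ratios are 3 v 12 months:

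- cardiovascular, no true effect: (0.1187 + 0.003s) / (0.1187 + 0.006s);
- non-cardiovascular A, only fatal bleeds differ: (0.0477 - 0.003s) / (0.0507 - 0.006s), where 0.0477 = 0.0507 - 0.003;
- non-cardiovascular B, with the 0.83 non-cardiac hazard ratio of Protocol 9.2 taken as a risk ratio: (0.0421 - 0.003s) / (0.0507 - 0.006s), where 0.0421 = 0.83 x 0.0507.

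| s | Deaths moved, 12 v 3 months | Share of 116 | Cardiovascular RR | RR A | RR B |
|---|---|---|---|---|---|
| 0 | 0 v 0 | 0% | 1.000 | 0.941 | 0.830 |
| 0.25 | 3.4 v 1.7 | 3.0% | 0.994 | 0.954 | 0.840 |
| 0.50 | 6.9 v 3.4 | 5.9% | 0.988 | 0.968 | 0.851 |
| 0.75 | 10.3 v 5.1 | 8.9% | 0.982 | 0.984 | 0.862 |

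The standard error of log RR is the square root of (1 - p1)/(n p1) + (1 - p0)/(n p0). The 95% limits are the RR divided and multiplied by about 1.17 (cardiovascular), 1.29-1.30 (A) and 1.30-1.32 (B). The largest shifts, at s = 0.75, are 0.34 of a standard error (A) and 0.23 (cardiovascular). With the protocol's 6% planning rate, the 12-month arm has 2,288 x 0.06 = 137 deaths and the share moved is 2.5-7.5%.

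**The case against.** The strongest reply is that assigning every I code to cardiovascular death is an explicit rule and largely a sound one. The endpoint covers cardiac and non-cardiac cardiovascular death. Protocol 7.1 puts fatal haemorrhagic stroke among the efficacy outcomes. SAP Appendix B codes I60-I62 as haemorrhagic stroke and I23 as ischaemic heart disease. This stands for I60-I62 and I23.0, so a reader should not infer that all ten codes are misplaced, nor that moving all ten out would be harmless. It does not cover I85.0 and I98.3, which the SAP itself lists as gastrointestinal bleeding. And if the rule is deliberate, the label needs changing.

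A reader might also infer that I-coded fatal bleeds are lost from both endpoints with that label. They are not: the admission list in the composite contains all ten codes.

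Nor is non-cardiovascular death clearly the only secondary safety endpoint made up of deaths alone. Protocol 9.3, repeated in SAP section 2, names bleeding death as a secondary outcome with its own hazard ratio, although the SAP 4.6 list does not carry it separately.

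Other endpoints keep these deaths. Major bleeding includes all ten codes. The intracranial row ("I60x , I61x , I62x , S06.5x , S06.6x") keeps I60-I62, and the gastrointestinal row keeps I85.0 and I98.3.

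Two planned items help in part. SAP 4.6 reports component counts. SAP 4.6.1 repeats the safety outcomes with codes in any position. The latter changes the position searched and not the list, does not touch the cardiovascular endpoints, and does not say whether cause-of-death fields are covered. If they are, it would also count a non-bleeding I-coded death as non-cardiovascular whenever a listed letter is secondary. The quality check in SAP section 5 compares codes with the SAP, so it would confirm these lists.

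Protocol Table 2 is background and does not define the endpoints. It supports the expectation of an exhaustive split but does not prove it. None of this explains the missing W.

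**Conclusion.** The point holds in two parts of unequal kind. The W gap is wrong as written: the definitions leave out one letter, and nothing in either document explains why. The I-code part is an inconsistency between label and codes in the standalone endpoint, clearest for I85.0 and I98.3, and only partial in the composite.

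Four secondary endpoints are touched: non-cardiovascular death, its composite with major non-fatal bleeding, cardiovascular death, and cardiovascular death or non-fatal infarction. All-cause mortality and the exploratory composite built on it are not.

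The I-code effect is small: about 3 v 2 to 10 v 5 deaths in the UK arms, and at most about a third of a standard error. It rests on the assumed 25-75% share, the 0.6% v 0.3% planning rates, UK numbers only, and Scottish rates whose coding the protocol does not describe. The number of W deaths cannot be derived from the documents. A reader might infer that the misallocation could reverse a cause-specific finding; these figures do not support that. The case for acting is that a prespecified endpoint should match its label, deaths should add up, and the correction is cheap.

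**What to change.** Make these changes before results by arm are seen.

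1. In both rows, define non-cardiovascular death as every death not classed as cardiovascular. This assigns W and makes the split exhaustive. State how a death with no recorded cause is handled, since the complement would take it in.
2. Make label and codes agree, in one of two ways. Either allocate each of the ten I codes, I85.0 and I98.3 in particular, in a documented table applied to both cardiovascular-death endpoints and both non-cardiovascular rows; or keep all I codes as cardiovascular and reword the label to say that I-coded fatal bleeds count there. Code-by-code allocation is safer than moving all ten, which would conflict with Protocol 7.1 and Appendix B. Report the alternative allocation as a sensitivity analysis.

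Two tidy-ups can go in the same revision but do not bear on the point. The gastrointestinal row ends "K62.5x , K55.2x , K66.1x", yet K55.2 is not in the master bleeding list. S06.4 is in the master list but not in the intracranial row.

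The cost is a short edit to Appendix C, a few lines of code and one recorded decision. No new data are needed.
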